Eligible participants will be scheduled for two study visits that will take place in the Clinical Research Unit (CRU) inpatient unit at the University of Wisconsin Hospital. Modifiable inclusion/exclusion criteria will be re-confirmed at both study visits by the above procedures as well as a medical history and physical exam. Participants will be randomly assigned to drug order (prazosin 1st vs. 2nd visit) in a stratified blocked schedule by sex and group (alcoholic vs. control) using urn randomization procedures⁸⁵. The randomization and double-blind will be implemented and maintained by the UW Pharmaceutical Research Center, which is located in the same building in the UW hospital as all study visits in the CRU. All participants are told that they will receive both 2mg of prazosin and placebo, one agent at each study visit. Drug/placebo order is counterbalanced between participants. However, neither participants nor researchers will be aware of whether prazosin or placebo is administered at each visit.

All subsequent procedures will be identical at the first and second study visits except for the assessment of study eligibility and the drug administered. Alcoholic participants will complete a brief alcohol craving questionnaire, a 6 item subset of the 14-item version of the Desires for Alcohol Questionnaire (DAQ⁸⁶) to determine baseline craving levels. Women of childbearing potential participants will provide a urine sample to verify they are not pregnant. All participants will then provide a breath sample to verify an initial blood alcohol concentration (BAC) of 0.00 (Alcosensor IV; Intoximeters, Inc.). All participants will be asked to refrain from consuming alcoholic beverages or any other psychoactive drugs for 24 hours prior to the experimental session, to avoid any acute effects of alcohol. Next all participants will ingest one pill with a full glass of water.

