Research assistants will then prepare the participant for the experimental task with physiological sensors. Next participants will complete a baseline assessment of their blink EMG response and a shock sensitivity rating as per standard procedures from our laboratory. Based on the known pharmacodynamics of prazosin⁸⁷, participants will begin the NPU task (see below) exactly 90 minutes after drug administration. During the stress-reactivity task participants will view geometric shapes and words presented on a computer monitor. Participants will be asked to answer short questions during this procedure, which will be audio recorded for later scoring for accuracy. At various times during this procedure, brief electric shocks will be administered to the fingers of the participants' hand. The intensity of all shocks will be within the range that they indicated they could tolerate during the shock sensitivity procedure. In addition, acoustic white noise probes will be presented through earphones at random points during the procedure. These probes are used to elicit a startle blink reflex, which is used to index emotional response. After completion of the task, participants will complete questionnaires related to their emotional state during the task and a battery of self-report questionnaires to assess alcohol use history, trait affect and broadband personality traits.

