After the NPU task participants will remain in the CRU inpatient unit overnight to monitor and assess for side effects under medical supervision by CRU staff. Participants second appointment will be scheduled 7 days (+/- 2 days) after the first study visit. Participants with unusable data at the first study visit (e.g., excessive physiological artifact, insufficient understanding of NPU task, startle non-responder) will not return for the second study visit. This study visit will be identical to the first study visit except for the drug administered (Prazosin vs. Placebo) and eligibility screening procedures. At the end of the first visit participants will be paid \$150. At the second visit participants will be paid \$150 for the study visit and a \$75 bonus for study completion, debriefed, and released. Participants who do not complete the study (e.g., not eligible, refuse consent, withdraw, etc.) will be paid \$25/hour for their time up to \$150/visit. Alcoholic participants will be required to demonstrate that they are not experiencing significantly elevated levels of alcohol craving (Desires for Alcohol Questionnaire) before they are released, per standard lab procedures.

Table 1: Overview of Study Procedures

CATEGORY	PROCEDURE	STUDY VISIT 1 (Day 1)	STUDY VISIT 2 (Day 4-10)
SCREENING			
Eligibility	Consent, Inclusion/exclusion criteria	X	
Medical history/assessment	Medical history, concomitant medications, vital signs	X	
Alcohol Use	Timeline follow back; SCID - Substance Use Disorder	X	
	Blood alcohol concentration (BAC; via breath test)	X	X
Lab Chemistry	Urine pregnancy test	X	X
SAFETY			
Visit safety	Vital signs; Medication side effects	X	X
Acute craving (for study release)	6 item subset from Desire for Alcohol Scale	X	X
DRUG ADMINISTRATION			
Drug	Prazosin or placebo	2 mg prazosin or placebo	2 mg prazosin or placebo
OUTCOMES			
Stress reactivity	Startle potentiation and self-report negative affect from NPU task	X	X
Individual difference moderators	Self report: alcohol dependence severity, trait affect, personality trait	X	

Participant Reimbursement

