All participants are paid \$15 for time spent in the lab during the screening visit. All participants are paid \$150/visit for time spent in the CRU for all study visits. Participants are provided a \$75 bonus for completing all study visits. Participants who do not complete the study (e.g., not eligible, refuse consent, withdraw, etc.) will be paid \$25/hour for their time at the CRU up to \$150/visit. These modest inducements represent reasonable compensation for time spent in the study and cannot be considered coercive.

Visit #	Time	Reimbursement
---------	------	---------------

Screening Visit	1 hour	\$15
Study Visit 1	3 to 5 hours + overnight	\$150
Study Visit 2	2 to 4 hours + overnight	\$150
Study Completion Bonus		\$75
Total		\$390 75

Statistical Analysis and Timeline

Statistical Analysis

Analyses for quantitative dependent measures will be accomplished within General Linear Models using R⁸⁸. In the sections below, we briefly describe the primary factors in statistical models to evaluate each Specific Aim. All models will include number of days abstinent at Visit 1 as an interactive between-subjects regressor to evaluate if drug effects and outcomes are comparable across alcoholics who vary in their previous duration of abstinence (1-8 weeks) on study initiation, although this has not moderated the effects on NPU task in our preliminary studies. Numerous individual difference measures (e.g., sex, mood/anxiety disorder comorbidity, tobacco use, trait affect, alcohol dependence severity) are available to add to these models as interactive between-subject regressors in secondary analyses to evaluate possible individual difference moderators of drug effects.

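### The trait-affect, personality and alcohol-history scales offered as moderators of the drug effect are completed after the dose and after the shock task

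*Combined protocol and SAP*

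**What the plan says.** The order of events at a study visit is set out in the protocol under Overview of Study Procedures. After the craving, pregnancy and breath checks: "Next all participants will ingest one pill with a full glass of water". Sensors and baseline startle follow, then "participants will begin the NPU task (see below) exactly 90 minutes after drug administration". The questionnaires come last: "After completion of the task, participants will complete questionnaires related to their emotional state during the task and a battery of self-report questionnaires". The content of that second set is given as "a battery of self-report questionnaires to assess alcohol use history, trait affect and broadband personality traits".

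Table 1 has a row for individual-difference moderators, "Self report: alcohol dependence severity, trait affect, personality trait", marked at Visit 1 only.

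The Statistical Analysis section says "Numerous individual difference measures (e.g., sex, mood/anxiety disorder comorbidity, tobacco use, trait affect, alcohol dependence severity) are available to add to these models", and that they would enter as "interactive between-subject regressors in secondary analyses to evaluate possible individual difference moderators of drug effects". The same section adds Drug Order to the models as an interactive between-subjects term.

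No administration of the trait or personality scales before dosing is described. The questionnaires mentioned for the screening visit serve to confirm eligibility.

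**The concern.** A moderator of a treatment effect should be fixed before treatment. Here the drug taken at Visit 1 is randomized, so about half the participants rate their trait affect on prazosin, and all rate it shortly after the shock task. Aim 1.2 predicts that prazosin lowers self-reported negative affect in response to the stressors. If some of that carries into the trait ratings, the moderator is partly an outcome. An apparent finding that prazosin works differently in people with high trait negative affect could then arise from the order of procedures. A score collected after dose and task cannot be made pre-treatment later.

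**Working it through.** The plan gives no figure on this point to reproduce. The check is of timing first, then of size under stated assumptions.

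**Which moderators are affected**
- Trait affect: in the post-task battery and named as a possible moderator. Affected.
- Personality: in the battery and in the Table 1 moderator row, but not among the examples in Statistical Analysis. Affected if used.
- Alcohol use history: in the battery. Alcohol dependence severity is the term in Table 1 and Statistical Analysis. That it is collected in the same battery is an inference, since the SCID substance use module is done at screening.
- Sex: a randomization stratum. Daily nicotine use and Axis I psychopathology: group-matching characteristics. None of the three is in the battery.
- Days abstinent, the regressor planned for all models, is defined at study start and is not from the battery.

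**Size for a Drug-by-moderator test (all inputs assumed except N = 72 and the two drug orders)**
Take 36 participants per order. Let D be a person's prazosin-minus-placebo difference, with SD 1 within order. Let T be the true trait, SD 1, unrelated to D, so the true moderation slope is 0. Let S be the person's drug responsiveness, SD 1, correlated h with D. The recorded score is M = T for those given placebo first, and M = T + g + kS for those given prazosin first. An order effect of 0.5 SD on D is included.

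1. *Uniform shift (k = 0), g = 0.2 to 0.5 SD.* Simulated false positives are 5.0% to 8.2% without Drug Order in the model and 4.7% to 5.1% with it. Drug Order handles this case.

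2. *Shift that follows drug response, Drug Order included.* Pooling within orders, the covariance of M and D is kh/2 and the variance of M is 1 + k²/2, so the spurious slope is (kh/2)/(1 + k²/2).
   - k = 0.3, h = 0.5: 0.075/1.045 = 0.072. Simulated slope 0.069 to 0.072, false positives 8.5% to 9.3%.
   - k = 0.5, h = 0.5: 0.125/1.125 = 0.111. Simulated slope 0.111, false positives 16.5%.
   - If the score tracks the measured drug difference itself (h = 1) with k = 0.1 to 0.3, the rate is 7% to 23%. Adding an Order-by-moderator term leaves 7% to 21%.

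3. *Carry-over from the task.* Let P and B be reactivity on prazosin and placebo, D = P − B, and let the score pick up c times Visit 1 reactivity. The covariance with D is c(Var P − Cov) in the prazosin-first order and c(Cov − Var B) in the other. The average over balanced orders is c(Var P − Var B)/2. This cancels if the two variances are equal. It does not cancel if prazosin narrows the spread, as it would if strong reactors gain most. The documents give no variances, so no rate is attached.

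4. *No effect of drug or task on the scales (g = k = c = 0).* The rate is the nominal 5%.

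**The case against.** The best defence is that these are trait and history scales, meant to be stable. The documents give no evidence that a single 2 mg dose moves them, and Aim 1.2 concerns the response to stressors. That stands as a reason to expect a small effect. It is not a reason to rely on stability when earlier administration makes the assumption unnecessary.

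Drug Order is in the model. This stands for a uniform shift, as step 1 shows, but not for step 2.

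The analyses are optional. The scales are only available to be added "in secondary analyses to evaluate possible individual difference moderators of drug effects", no specific test is promised, and the plan does not call the scores baseline values. This stands, and it limits the importance of the point.

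Table 1 is weak evidence on timing. It has no screening column and lists consent and the SCID under Visit 1. This also stands: the timing rests on the prose in Overview of Study Procedures.

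Two stronger readings are tempting. A reader might infer that every individual-difference moderator is post-treatment; three of the five named examples are not in the battery. A reader might also correlate the scores with Visit 1 reactivity. If 5% to 20% of score variance comes from the session and that part correlates .3 to .5 with reactivity, the spurious correlation is √.05 × .3 = .067 to √.20 × .5 = .224, with false-positive rates of about 9% to 48%. That is not the planned analysis. The plan proposes moderators of drug effects in two-visit models, where Drug is a repeated factor and much of this carry-over cancels across balanced orders.

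**Conclusion.** The point holds in a limited form and is a cheap improvement, not a threat to the trial's main conclusions. By the stated order of procedures, trait affect, personality and alcohol use history (and dependence severity, if it is collected there) are post-treatment when used to moderate drug effects. The planned model protects against a uniform drug shift only. For a shift that follows individual drug response, about 9% to 17% false positives at a nominal 5% is a fair illustration. It rests on assumed values (k = 0.3 to 0.5, h = 0.5) that the documents neither support nor exclude. The documents do not show that the scales move at all, and if they do not, there is no bias.

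**What to change.** In Overview of Study Procedures and Table 1, place the trait-affect, personality and alcohol-history or severity questionnaires before the pill at Visit 1, or at the drug-free screening visit. Leave only the questionnaires about emotional state during the task after it. State where dependence severity is collected. Reconcile the statement that the two visits are identical apart from eligibility assessment and drug with Table 1, which marks the battery at Visit 1 only. If the timing cannot change, state the limitation wherever these moderator results are reported.

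No new instrument is needed. The cost is a somewhat longer session. Screening is listed at 1 hour and $15 and already holds consent, interviews, the SCID module, vital signs, the pregnancy test and the shock rating, so its stated length and payment may need adjusting. Placing the battery before the dose at Visit 1 avoids that.

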Unpredictable startle potentiation and self-reported negative affect from the NPU task across Visits 1-2 will be analyzed in separate general linear models with repeated measures on Drug (2 mg prazosin vs placebo) and Condition (unpredictable vs. predictable shock). Participant Group (alcoholic vs. control) and Drug Order (prazosin: visit 1 vs visit 2) will also be included as an interactive between subjects regressors to increase power. **Specific Aim 1** predictions will be supported by significant Drug X Condition interactions with prazosin producing selectively larger reduction in startle potentiation and self-reported negative affect during unpredictable relative to predictable shock. **Specific Aim 2** predictions will be supported by significant Group X Condition interactions with abstinent alcoholics displaying selectively larger startle potentiation and self-reported negative affect during unpredictable relative to predictable shock. **Specific Aim 3** predictions will be supported by significant Drug X Group X Condition interactions with prazosin producing selectively larger reduction in startle potentiation and self-reported negative affect during unpredictable relative to predictable shock to a greater degree among abstinent alcoholic than control participants.

Power Analyses for Sample Size Justification

Power analyses were conducted using the pwr package in R which calculates power based on the approach outlined by Cohen⁸⁹. Power analyses were conducted to provide adequate power to detect comparable effect sizes observed in previous research from our laboratory that has used variants of the NPU task to examine acute drug effects (i.e., moderate dose of alcohol), drug deprivation effects (24 hours of nicotine deprivation among daily smokers), or differences between alcoholics in early abstinence (1-8 weeks) vs. matched controls. In the current study, N = 72 will provide 85% power to detect the effect of prazosin on startle potentiation during unpredictable (vs. predictable) stress in alcohol dependent participants (vs. controls) assuming a conservative small effect size ($\Delta R^2 = .10$) in a model containing the predictors noted above ($R^2 = .30$).

Timeline Justification

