This project aims to be completed within three years. This goal is reasonable given our team's expertise in conducting psychophysiological laboratory research working with drug administration (i.e., alcohol and nicotine), community participants, and stress reactivity. Our lab has the experience and infrastructure to recruit and retain a sample of this size. We recently completed a pilot study for the current application that recruited 115 participants (58 alcoholic and 57 matched controls) over the course of 14 months. This study involved diagnostic interviews and stress-reactivity task over the course of two study visits. The current study will plan to initially consent eighty-five participants with a final sample size goal of seventy-two participants. Based on prior experience we anticipate that 85% of eligible participants will return to complete all study visits. A total of 157 complete visits (85 first, 72 second) will be conducted. If we conservatively expect to average 2 study visits per week to account for no-shows, failed eligibility criteria, and equipment failure we anticipate completing data collection within 1.5-2 years.

Reference Cited

1. Erb, S. *et al.* Alpha-2 adrenergic receptor agonists block stress-induced reinstatement of cocaine seeking. *Neuropsychopharmacology* **23**, 138–50 (2000).
2. Pacák, K. *et al.* Effects of various stressors on in vivo norepinephrine release in the hypothalamic paraventricular nucleus and on the pituitary-adrenocortical axis. *Ann. N. Y. Acad. Sci.* **771**, 115–130 (1995).
6. Pacák, K. *et al.* Effects of single or repeated immobilization on release of norepinephrine and its metabolites in the central nucleus of the amygdala in conscious rats. *Neuroendocrinology* **57**, 626–633 (1993).

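### The repeated-measures model for all three aims conventionally needs both visits, and the plan does not say what happens to a usable first visit without a second

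*Combined protocol and SAP*

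**What the plan says.** All references are to the combined protocol and SAP.

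- **Statistical Analysis** sets the model family: "Analyses for quantitative dependent measures will be accomplished within General Linear Models using R". Startle potentiation and self-reported negative affect across Visits 1 and 2 "will be analyzed in separate general linear models with repeated measures on Drug (2 mg prazosin vs placebo) and Condition". For the between-person side, "Participant Group (alcoholic vs. control) and Drug Order (prazosin: visit 1 vs visit 2) will also be included as an interactive between subjects regressors". Days abstinent at Visit 1 also enters all models interactively. Aim 1 is read from Drug X Condition, Aim 2 from Group X Condition and Aim 3 from Drug X Group X Condition.
- **Timeline Justification** gives the numbers. The plan is to enrol 85 people so as to finish with 72, on the expectation that 85% of those eligible come back. The visit count is then put as follows: "A total of 157 complete visits (85 first, 72 second) will be conducted".
- **Power Analyses for Sample Size Justification** claims 85% power at N = 72.
- **Overview of Study Procedures** adds a rule: "Participants with unusable data at the first study visit" do not come back for the second. The examples given are artefact, failure to grasp the task and absence of a startle response.

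No section names a mixed model, an analysis set or a rule for a participant with one visit.

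**The concern.** Drug is a within-person factor and each visit carries one level of it. A conventional repeated-measures general linear model needs both levels from each person, so someone with a good first visit who does not return contributes to none of the three aims.

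Two things are at stake. The first is precision. A single visit says little about a within-person drug effect. It does contain a full unpredictable-versus-predictable comparison, though, and so bears directly on the group difference in Aim 2.

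The second is selection. If return depends on how a person responded at Visit 1, the completers are a selected sample and the group comparison can shift. A likelihood-based model that keeps the Visit 1 data needs only the weaker condition that data are missing at random given what was observed.

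**Working it through.** **1. The plan's own figures.** 72/0.85 = 84.7, rounded up to 85. 85 × 0.85 = 72.25. 85 + 72 = 157 visits. 85 − 72 = 13 first visits without a second. All agree with Timeline Justification.

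**2. The stated power.** Inputs: ΔR² = .10 and R² = .30 from the power section; alpha .05 is assumed, as none is given. f² = .10/(1 − .30) = 0.143. Group, Drug Order and days abstinent, fully interactive, use 2 × 2 × 2 = 8 between-person parameters, so v = 72 − 8 = 64. With λ = f²(1 + 64 + 1) = 9.43, a 1-df F test has power 85.6%. The claim therefore reproduces on 72 completers.

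**3. How many single visits are usable.** Non-return includes people stopped for unusable Visit 1 data, and the documents do not split the 13. The usable number lies between 0 and 13. The calculation below takes 13 and, as an assumed midpoint, 6.5.

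**4. Precision recovered.** Work on the within-visit contrast (unpredictable minus predictable). Its drug difference is Drug X Condition and its group difference averaged over visits is Group X Condition. Let m = 72 completers, n = 72 plus usable singles, and ρ = the between-visit correlation of the contrast (not in the documents; .3 to .7 assumed). With a free mean for each drug order and visit, equal variances and balanced groups, the maximum-likelihood variance relative to completers only is:

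- drug contrasts: [(1 − ρ)m/n + (1 + ρ)]/2
- Group X Condition: [(1 + ρ)m/n + (1 − ρ)]/2

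Example with 13 singles and ρ = .7: m/n = 72/85 = .847; group ratio = (1.7 × .847 + .3)/2 = .870; SE ratio = √.870 = .933; equivalent completers = 72/.870 = 82.8.

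| Usable singles | ρ | SE ratio, Group X Condition | Equivalent completers, Aim 2 | SE ratio, drug contrasts |
|---|---|---|---|---|
| 6.5 | .3 | .973 | 76.1 | .985 |
| 6.5 | .7 | .964 | 77.5 | .994 |
| 13 | .3 | .949 | 79.9 | .973 |
| 13 | .7 | .933 | 82.8 | .989 |

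For the powered test (Aim 3), adding all 13 moves power from 85.6% to 87.5% (ρ = .3) or 86.4% (ρ = .7). With no usable singles every ratio is 1.

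**5. Selection, Aim 2.** Suppose 15% are lost in one group only, ρ = .5, and the odds of non-return rise 2.7-fold per SD of the Visit 1 contrast (all assumed). Simulated returners are then about 0.13 SD low at Visit 1 and ρ times that at Visit 2, so their two-visit mean is off by 0.13 × (1 + .5)/2 ≈ 0.10 SD. The likelihood estimate using all Visit 1 data showed no shift.

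**6. Selection, drug contrasts.** Take a true drug effect of −0.30 and about 15% non-return. Simulated completers' estimates stay at about −0.29 to −0.30 when non-return depends on the Visit 1 drug, on stable reactivity or on the Visit 1 response. They move clearly, to about −0.33 to −0.36 according to the strength assumed, only when non-return depends on the response under prazosin alone.

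**The case against.** **The exclusion is inferred.** This stands. The section sets out only to sketch the main model factors, and nowhere says that one-visit participants are removed. The inference rests on the model form and on the powered N being equal to the number of second visits. If the sponsor intends something else, the text still needs to say so.

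**The usable count may be nil.** This also stands. A reader might infer that 13 good first visits are thrown away, because the retention sentence speaks of people returning and the visit count calls all 157 visits complete. The documents do not support that: unusable data is itself a listed cause of not returning, so 13 is only a ceiling.

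**No planned power is lost.** Correct. The study consents 85 in order to reach 72 and is powered on 72. Aim 2, where the gain is larger, is framed as confirming earlier findings.

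**Completers-only analysis is not generally biased here.** Largely right for Aims 1 and 3, where the contrasts are within person and Drug Order and Group are already in the model (step 6). It does not dispose of Aim 2, a between-person comparison.

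**A repeated-measures model is valid for a two-visit crossover.** True. But the mixed model handles the same hypotheses in the same software, protects Aim 2 under a weaker condition and costs little, so the request is more than a matter of taste.

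**Conclusion.** The point holds as a cheap improvement. Followed in its conventional form, the plan analyses completers only for all three aims and drops any usable first visit without a second.

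If 6.5 to 13 such visits exist and ρ is .3 to .7, including them lowers the standard error by about 3% to 7% for Aim 2 (like having about 76 to 83 completers instead of 72) and by about 1% to 3% for Aims 1 and 3. Fewer usable visits shrink the gain, to zero at the limit. These figures assume equal variances and balanced groups.

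A reader might go further and conclude that the trial is underpowered or that every aim is biased. Neither follows: 85% power reproduces on 72, and the drug contrasts are robust to most forms of selective return. The selection risk is chiefly for Aim 2, and nothing in the documents shows that it will occur. Nor is the mixed model a complete remedy: if return depends on something unobserved after Visit 1, missing at random fails as well.

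**What to change.** In Statistical Analysis:

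1. Define the analysis set as every randomised participant with at least one usable visit, and say what makes a visit usable.
2. Fit a linear mixed model in R with the fixed effects already listed: Drug, Condition, Group, Drug Order and their interactions, and days abstinent as planned. Do not add a separate period term. With two visits, Drug X Drug Order already is the visit effect: intercept, Drug, Drug Order, Drug X Drug Order and period make five columns of rank four.
3. Fix the covariance in advance, in a form that does not force one common variance on the Drug and Drug X Condition contrasts. An unstructured matrix would do. So would a mixed model on the within-visit unpredictable-minus-predictable contrast with a participant intercept. A participant intercept and Condition slope alone would impose the common variance.
4. Keep the completers general linear model as a sensitivity analysis.
5. Report non-return by group and drug order, with reasons, separating unusable data from failure to return.

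Cost: a few sentences of SAP text, a covariance choice made in advance and slightly more analysis work. No participant, visit or assessment changes.

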- *Stimulants (e.g., d-amphetamine, methylphenidate) or alternative medications with stimulant properties (e.g., ephedra). [Excluded because these medications directly alter CNS noradrenergic neurotransmission.]
- *Beta-blockers (e.g., propranolol), alpha2 agonists (e.g., clonidine, guanfacine), and SNRI anti-depressants (e.g., venlafaxine, duloxetine). [Excluded because these medications directly alter CNS noradrenergic neurotransmission.]

Note: Women of childbearing potential are females who have experienced menarche and do not meet the criteria for women **not** of childbearing potential. Women **not** of childbearing potential are females who are permanently sterile (e.g., hysterectomy, bilateral oophorectomy) or postmenopausal. Postmenopausal is defined as 12 consecutive months with no menses without an alternative medical cause.

Research Design and Methods Overview

Overview of Study Procedures

Seventy-two participants (36 alcoholic & 36 controls) will be recruited to participate in a double-blind, placebo-controlled, mixed-design, cross-over study examining the effects of a NE- α 1 antagonist (prazosin) on the affective response to stressors. ~~Both study visits will take place in the Clinical Research Unit (CRU) inpatient unit at the University of Wisconsin Hospital. A screening visit will take place in the Addiction Research Center at the University of Wisconsin – Madison.~~ At the first study screening visit general laboratory procedures and risks and benefits will be explained to the participants and informed consent will be obtained from all participants. Inclusion/exclusion criteria will be confirmed using interviews conducted by a nurse, graduate level clinician, self-report questionnaires and urine test for pregnancy. ~~Study Nursing~~ staff will collect ~~a medical history~~, current medication, orthostatic vital signs, and urine pregnancy test to confirm eligibility. For both participant groups, research staff will first confirm that the potential participant is free from severe and persistent mental illness. Following this, the more in-depth Substance Use Disorders Module of the SCID-Research Version (SCID-RV⁸⁴) will be administered to confirm the alcoholic participants' status with respect to an Alcohol Dependence diagnosis and no lifetime history of substance dependence for control participants. Participants will complete a shock sensitivity rating as per standard procedures from our laboratory.

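### Sex stratifies the randomisation of drug order but is left out of the primary models without a reason; adding it as a covariate is a nearly free, minor improvement.

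*Combined protocol and SAP*

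**What the plan says.** The trial is a "double-blind, placebo-controlled, mixed-design, cross-over study" in which each participant takes prazosin at one visit and placebo at the other (Overview of Study Procedures). What is randomised is therefore the order of the two, and this is done "in a stratified blocked schedule by sex and group (alcoholic vs. control) using urn randomization procedures". Under Participant Population and Recruitment, sex is also one of the characteristics on which the alcoholic and control groups are matched at group level.

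Statistical Analysis specifies "general linear models with repeated measures on Drug (2 mg prazosin vs placebo) and Condition (unpredictable vs. predictable shock"). On the between-subjects side, "Participant Group (alcoholic vs. control) and Drug Order (prazosin: visit 1 vs visit 2) will also be included as an interactive between subjects regressors", and "All models will include number of days abstinent at Visit 1 as an interactive between-subjects regressor". Sex is not in this list. It is named only in the sentence beginning "Numerous individual difference measures (e.g., sex, mood/anxiety disorder comorbidity, tobacco use, trait affect, alcohol dependence severity) are available to add to these models", which ends "as interactive between-subject regressors in secondary analyses to evaluate possible individual difference moderators of drug effects". The plan does not say why one stratification factor is modelled and the other is not.

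**The concern.** A factor used to stratify the allocation normally belongs in the primary model. Stratifying on it makes the estimate more precise, but a model without it leaves its variance in the residual, so the reported standard error is too large and the test conservative. The plan treats sex as important enough to stratify on, to match on and to list as a possible moderator. It includes Group and Drug Order explicitly to gain power, and puts days abstinent in every model although the preliminary studies showed no moderation by it. Leaving sex out is hard to square with that approach. What is at stake is a small amount of power, not the validity of the comparison.

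**Working it through.** **1. The plan's own power figure.** Inputs from Power Analyses for Sample Size Justification: N = 72, increment in R² of .10, model R² of .30, stated power 85%. Assumed, because the plan does not state them: alpha .05, a 1-df F test, and p between-subjects predictors.

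- f² = .10 / (1 − .30) = 0.143; u = 1; v = 72 − p − 1; noncentrality λ = f²(u + v + 1), the convention of the pwr package.
- p = 7: v = 64, λ = 0.143 × 66 = 9.43, power 85.6%.
- p = 5 gives 86.7% and p = 8 gives 85.1%. The stated 85% is reproduced.

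**2. Cost of adding sex if it explains nothing.** One more predictor takes v from 64 to 63, λ = 0.143 × 65 = 9.29, and power from 85.6% to 85.1% (86.7% to 86.2% from p = 5). This is an upper figure, since the pwr convention shrinks λ with each predictor. With λ held at f² × 72, power goes from 88.47% to 88.45%.

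**3. Where sex can matter.** For each participant let D = (unpredictable − predictable on prazosin) − (unpredictable − predictable on placebo). Aim 1 tests the mean of D; Aim 3 tests its difference between groups. A sex difference in startle level, or in unpredictable-minus-predictable potentiation, is the same at both visits and cancels from D. It stays in D only if sex modifies the drug effect or the period effect. Aim 2 tests the group difference in the participant's average unpredictable-minus-predictable contrast, where a sex effect on that contrast does not cancel.

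**4. Size when sex does matter.** Assume equal numbers of each sex, order balanced within sex and group, and a sex difference of 0.5 SD on the tested contrast.

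- Variance left in the residual: (0.5/2)² = 0.0625, in units of the residual variance with sex in the model.
- Reported standard error too large by √1.0625 = 1.031, about 3%.
- The critical value becomes in effect 1.96 × 1.031 = 2.02, so the true type I error is about 4.3%, below 5%.

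Simulation, 50,000 runs per setting, 72 participants, true effects set to give about 85% power:

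| Setting | Without sex | Sex as a single term | Sex with Group and Order interactions |
|---|---|---|---|
| Aims 1 and 3, sex main effect only | 85.4–85.6% | 85.3–85.6% | 85.3–85.6% |
| Aims 1 and 3, sex-by-drug 0.5 SD | 83.5–83.6% | 85.1% | 85.0–85.1% |
| Aims 1 and 3, sex-by-period 0.5 SD | 83.9% | 83.9% | 85.3–85.4% |
| Aim 2, sex effect 0.5 SD | 83.8% | 85.3% | not run |

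Type I error without sex was about 5% in the first row and 4.1–4.3% in the others. The loss is about 1.5 points, and a single sex term recovers it except for a sex-by-period effect.

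**5. Cost of full crossing.** If sex is crossed with all the other between-subjects terms and explains nothing, the formula in step 1 gives 83.4% (5 to 11 predictors) or 80.8% (7 to 15). The λ caveat in step 2 applies here too: with λ fixed, the second case is 88.3%.

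**The case against.** The strongest reply is that parallel-group reasoning does not carry over to a cross-over. Each participant is their own control, so for Aims 1 and 3 a sex effect on startle is removed by design. The randomised factor, drug order, and the other stratification factor, group, are both modelled. All of this stands. A reader might infer from the missing term that the analysis does not follow the randomisation, or that precision is discarded for all three aims. The first is too strong, because one of two strata is omitted and nothing else. The second fails because Aims 1 and 3 lose precision only if sex modifies the drug (or period) effect, while Aim 2 compares groups that are not randomised at all.

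A second reply is that any sizeable gain has to be assumed. That also stands. With 7 predictors, adding sex raises power only if it explains more than about 1.1% of the variance. Shares of 2%, 5% and 10% would give 86.1%, 87.6% and 90.0%, from f² = .10/(.70 − share). A reader might take the last as attainable, but it would need sex to explain as much of the drug contrast as the effect the trial is powered for. The documents give no sex effect of any size.

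Nor is primary use of sex left to a later choice: the plan confines it to secondary moderator analyses. What the replies do not supply is a reason for leaving out a factor the trial stratifies on and already records.

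**Conclusion.** The mismatch is real and minor. Under balance there is no bias and no inflated type I error; the tests are, if anything, slightly conservative. The loss is about 1.5 points of power under an assumed 0.5 SD sex effect on the tested contrast, and none for Aims 1 and 3 if sex affects only the level of startle or of potentiation. The price of adding sex is at most about half a point.

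This rests on alpha .05, 7 predictors, equal numbers of each sex and order balanced within strata. Urn randomisation and group-level matching give only approximate balance, and 85 participants are to be consented for 72 completers. If the completers' sex mix differed between groups, a sex effect could also enter the group comparisons. The documents do not indicate that this will happen, so it is a further reason for the covariate and not a demonstrated flaw.

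**What to change.** Add one sentence to Statistical Analysis: sex enters every primary model as a between-subjects covariate, centred at the sample mean, together with its interactions with Drug, Condition and Drug X Condition. Centring keeps the drug effect an average over the participants studied. The interactions with the within-subject factors are what let sex act on the tested contrasts; a sex main effect alone would not.

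Do not cross sex with Group, Drug Order or days abstinent in the primary model. On the plan's own power method full crossing could take power to about 81–83% if sex explains nothing. Keep sex-by-order (period) terms and Sex X Drug X Group moderation in sensitivity or secondary analyses.

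The cost is one sentence and one degree of freedom per tested contrast. It needs no new data and no change to the sample size.
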